**Rationale/background for changes:**

- A tertiary objective was added to allow potential exploratory evaluation of immune responses induced by the study vaccine(s) against a panel of strains of *Neisseria* species in a subset of subjects.
- Protocol Clarification Letter 1 was incorporated, which removed reference to a pregnancy electronic case report form.
- The window for Subject Diary reminder calls was clarified.
- Other minor changes were made to correct typos, and improve clarity and alignment within the document.

Minor administrative edits (e.g. typos, abbreviations) have not been listed here.

**Amended text has been included in *bold italics* and deleted text in ~~strikethrough~~ in the following sections:**

Synopsis, ObjectivesTertiary

- *To further characterize the immune response induced by the study vaccine(s) against an additional panel of strains of *Neisseria* species in a subset of subjects.*

*Note: This tertiary objective is exploratory and suitable assays may or may not be developed. The tertiary objective will be assessed in a subset of subjects using remaining serum after the primary and secondary analyses have been completed; no additional blood samples will be collected from subjects. Any outcome of exploratory testing that would be of scientific/medical relevance will be reported in an annex/addendum to the final study report.*

Synopsis, Method of evaluation**Tertiary**

- *Endpoints related to the tertiary objective will be described in a separate statistical analysis plan.*

Section 2.3 Tertiary objective (newly added header and section)**2.3 Tertiary objective**

- *To further characterize the immune response induced by the study vaccine(s) against an additional panel of strains of Neisseria species in a subset of subjects.*

*Note: This tertiary objective is exploratory and suitable assays may or may not be developed. The tertiary objective will be assessed in a subset of subjects using remaining serum after the primary and secondary analyses have been completed; no additional blood samples will be collected from subjects. Any outcome of exploratory testing that would be of scientific/medical relevance will be reported in an annex/addendum to the final study report.*

*Refer to Section 10.3 for the definition of the tertiary endpoint and to Section 10.11.1 for the reporting of tertiary endpoint results.*

Section 5.6.13.2.1 Subject diary reminder calls

Subject Diary reminder calls will be performed at 3 and 5 days ( $\pm 1$  day) after each vaccination (*i.e., Day 4 and Day 6 after the first vaccination and accordingly after the second vaccination*). The purpose of this call is to remind the subject/subject's parent(s)/LAR(s) about completion of the Subject Diary. The call follows the Subject Diary Reminder Telephone Call Script provided to the site. The subject/subject's parent(s)/LAR(s) should be reminded to contact the site via the telephone number provided in the informed consent to discuss medical questions.

Section 8.4.4 Completion and transmission of pregnancy reports

Once the investigator becomes aware that a subject is pregnant, the investigator (or designate) must complete the required information onto the paper pregnancy report **WITHIN 2 WEEKS**. The investigator (or designate) must complete and fax a pregnancy notification form to PPD Pharmacovigilance (at **PPD** ) after entering or updating information within the **paper** pregnancy **report** eCRF.

Section 10.3 Tertiary endpoint (newly added header and section; heading numbers were updated in subsequent sections accordingly)

### **10.3 Tertiary endpoint**

*Endpoints related to the tertiary objective will be described in a separate statistical analysis plan.*

#### Section 10.5.2 All Exposed Set

All subjects in the All Enrolled Set who receive a **any** study vaccination.

#### Section 10.5.4.1 Full Analysis Set 1

All subjects in the All Exposed Set who provided evaluable serum samples and whose assay results are available for at least 1 serogroup **or B strain** at Visit 4 for all study groups except the MenACWY group, or at Visit 2 for the MenACWY group.

#### Section 10.5.4.2 Full Analysis Set 2

All subjects in the All Exposed Set who provided evaluable serum samples and whose assay results are available for at least 1 serogroup **or B strain** at Visit 2 for all study groups except the MenACWY group.

#### Section 10.5.4.3 Full Analysis Set 3

All subjects in the All Exposed Set who provided evaluable serum samples and whose assay results are available for at least 1 serogroup **or B strain** at Visit 4 for all study groups except the MenACWY group, or at Visit 2 for the MenACWY group, and at baseline for all study groups.

#### Section 10.5.4.4 Full Analysis Set 4

All subjects in the All Exposed Set who provided evaluable serum samples and whose assay results are available for at least 1 serogroup **or B strain** at Visit 2 and at baseline for all study groups except the MenACWY group.

#### Section 10.11.1 Sequence of analyses

*Any outcome of exploratory testing will be reported in an annex/addendum to the final study report.*

## List of Abbreviations

AE	Adverse event
AESI	Adverse events of special interest
ANCOVA	Analysis of covariance
BMI	Body mass index
CI	Confidence interval
CSR	Clinical Study Report
eCRF	Electronic case report form
FASx	Full Analysis Set (x = 1, 2, 3, 4)
GMR	Geometric mean ratio
GMT	Geometric mean titer
GSD	Geometric standard deviation
GSK	GlaxoSmithKline
GSKDrug	GSK Drug Dictionary
hSBA	Serum bactericidal assay using human complement
IM	Intramuscular(ly)
IMD	Invasive meningococcal disease
LAR	Legally Acceptable Representative
LLOQ	Lower limit of quantitation
LOD	Limit of detection
MAR	Missing at random
MATEX	MATerial Excellence
MCAR	Missing completely at random
MedDRA	Medical Dictionary for Regulatory Activities
NC	Not calculated
pDiary	Paper diary
PPSx	Per Protocol Set x (x = 1, 2, 3, 4)
SAE	Serious adverse event
SBIR	Source DataBase for Internet Randomization
SD	Standard deviation
SE	Standard error

## 1 Introduction

Invasive meningococcal disease (IMD) occurs when, following an average incubation period of 4 days (range: 2 to 10 days), the normally asymptotically carried encapsulated gram-negative bacterium *N. meningitidis* enters the bloodstream and multiplies, potentially causing sepsis. If the bacteria cross the blood-brain barrier, meningitis occurs. Sepsis and meningitis caused by *N. meningitidis* are serious diseases that can be fatal or leave permanent sequelae. In European Union/European Economic Area countries, despite the availability of advanced medical treatment and effective antibiotics, case-fatality rates are high at approximately 7% to 15%, with most cases caused by serogroup B [ECDC, 2016]. Up to one fifth of survivors suffer long-term sequelae, including mental retardation, hearing loss, and loss of limb use [ECDC, 2016].

GlaxoSmithKline (GSK) Biologicals is developing a combination vaccine intended for primary immunization against *N. meningitidis* serogroups A, B, C, W-135, and Y (MenABCWY vaccine). The availability of a meningococcal vaccine based on the combination of antigens in 2 separate vaccines against serogroups ACWY (*Menveo*) and B (*Bexsero*) in a single vaccine/administration would reduce the number of injections and allow greater flexibility in dose administration schedules, and could increase coverage for meningococcal disease caused by *N. meningitidis* serogroups A, B, C, W-135, and Y worldwide.

MenACWY is a meningococcal oligosaccharide conjugate vaccine licensed for active immunization to prevent IMD caused by *N. meningitidis* serogroups A, C, W-135, and Y. The rMenB+OMV NZ vaccine provides active immunization to prevent IMD caused by *N. meningitidis* serogroup B. The investigational MenABCWY combination vaccine is based upon the 2 aforementioned and well established GSK Biologicals' vaccines, MenACWY and rMenB+OMV NZ.

In a recent Phase IIb study MenABCWY-011 (V102\_15), non-inferiority in terms of geometric mean titers (GMTs) could not be shown for 2 doses of MenABCWY versus 2 doses of rMenB+OMV NZ, given 2 months apart. Across several other studies of the MenABCWY program, immune responses against serogroup B antigens were also lower than immune responses assessed when rMenB+OMV NZ was administered alone. One possible reason that has been theorized is biological immune interference, possibly due to immunological stress to the lymph nodes in the arm where the combination vaccine is administered. The purpose of the current study is to evaluate whether there is immune interference when MenABCWY (consisting of MenACWY lyophilized component and rMenB+OMV NZ liquid component) is administered to healthy adolescents and adults following a 2-dose vaccination schedule with MenABCWY administered 2 months apart.

## 2 Objectives

### 2.1 Primary Objective

To assess the immune response to 2 doses of MenABCWY, rMenB+OMV NZ, or rMenB+OMV NZ and MenACWY administered concomitantly in the same arm or in 2 different arms, and to a single dose of MenACWY at 1 month after the last vaccination.

### 2.2 Secondary Objectives

#### Immunogenicity Objective

To assess the immune response to 2 doses of MenABCWY, rMenB+OMV NZ, or rMenB+OMV NZ and MenACWY administered concomitantly in the same arm or in 2 different arms at 1 month after the first vaccination.

#### Safety Objective

To assess the safety and tolerability of 2 doses of MenABCWY, rMenB+OMV NZ, or rMenB+OMV NZ and MenACWY administered concomitantly in the same arm or in 2 different arms, and to a single dose of MenACWY.

## 3 Investigational Plan

### 3.1 Overall Study Design and Plan

This is a Phase II, randomized, open-label, controlled, multi-centric study with 5 parallel study groups. The enrollment will be performed to ensure equal distribution of the population across two age strata of 10 to 17 years and 18 to 25 years in each study group. Within each stratum the randomization algorithm will use a minimization procedure accounting for center. Approximately 500 subjects will be randomly assigned at a 1:1:1:1:1 ratio to one of five study groups:

[figure not shown]
1. MenABCWY: Approximately 100 subjects (50 subjects aged 10 to 17 years and 50 subjects aged 18 to 25 years) will receive 1 intramuscular (IM) dose of MenABCWY twice, 2 months apart.
2. rMenBOMV+ACWY\_S: Approximately 100 subjects (50 subjects aged 10 to 17 years and 50 subjects aged 18 to 25 years) will concomitantly receive 1 IM dose of rMenB+OMV NZ and 1 IM dose of MenACWY in the same arm (approximately 2.5 cm apart) twice, 2 months apart.
3. rMenBOMV+ACWY\_D: Approximately 100 subjects (50 subjects aged 10 to 17 years and 50 subjects aged 18 to 25 years) will concomitantly receive 1 IM dose of rMenB+OMV NZ and 1 IM dose of MenACWY in 2 different arms twice, 2 months apart.

4. rMenBOMV: Approximately 100 subjects (50 subjects aged 10 to 17 years and 50 subjects aged 18 to 25 years) will receive 1 IM dose of rMenB+OMV NZ twice, 2 months apart.
5. MenACWY: Approximately 100 subjects (50 subjects aged 10 to 17 years and 50 subjects aged 18 to 25 years) will receive 1 IM dose of MenACWY once.

Details of the injection site location(s) can be found in Table 9.

The study design diagram is provided in Figure 1.

**Figure 1 Study Design**

The duration of the study is up to 91 days with subjects attending 4 visits, 30 days apart, starting at Visit 1 (Day 1) and ending at Visit 4 (Day 91). Whenever possible, the investigator should arrange study visits within the intervals described in Table 1. Visits that occur outside of the intervals will be categorized as significant protocol deviations leading to the exclusion of a subject from one of the Per Protocol sets (PPSx).

A detailed list of study procedures can be found in Section 11.2.

The signed/witnessed/thumb printed informed consent of the subject/subject's parent(s)/legally acceptable representative(s) (LARs) must be obtained before study participation. The signed informed assent of the subject below the age of consent (i.e. minor) should be obtained in addition to the signed informed consent by his/her parent(s)/LAR(s) according to local rules and regulations.

On Visit 1 (Day 1) or up to 5 days before Visit 1 (where allowed according to Table 1) informed consent will be obtained and pre-vaccination procedures will be carried out. Upon satisfactory completion of pre-vaccination procedures, subjects will be allocated a study group and treatment number and will have blood samples drawn before receiving the first dose of study vaccine(s).

Subjects will be observed closely for at least 30 minutes following the administration of the vaccine(s), with appropriate medical treatment readily available in case of anaphylaxis. Solicited adverse events (AEs) will be recorded during this 30 minute period (see Section 9.1.1 for details of solicited AEs).

Subjects will have a second dose of study vaccine(s) administered at Visit 3 (with the exception of the MenACWY group who only receive a single dose at Visit 1) following satisfactory completion of pre-vaccination procedures. Subjects will have blood drawn at Visit 1, Visit 2 and Visit 4 (with the exception of the MenACWY group who will only have blood drawn at Visit 1 and Visit 2) to test for immune response within the serogroups.

Unsolicited AEs will be recorded for 30 days following administration of study vaccine. AEs will be recorded starting from informed consent date if a separate visit occurs before Visit 1 (maximum 5 days before first dose of study vaccine). Serious adverse events (SAEs), medically attended AEs, AEs/SAEs leading to withdrawal, SAEs related to study participation or concurrent GSK medication/vaccines and adverse events of special interest (AESIs) will be recorded from the date of informed consent through Visit 4 (MenACWY group will have AEs recorded through Visit 2). Subjects will receive a safety follow-up call 14 days (or within 11 days - 17 days) after each visit where study vaccine is administered. Solicited AEs will be recorded in subject diaries by the subject/subject's parent(s)/LAR(s) for 7 days after the vaccine is administered (including the day on which the vaccine is administered).

**Table 1 Visit Intervals**

Interval	Optimal length of interval	Allowed interval (Min – Max) 
Visit 1 (Day 1) → Safety call 1 (Day 15)	14 days	11 days – 17 days (Days 12 – 18)
Visit 1 (Day 1) → Visit 2 (Day 31)	30 days	23 days – 40 days (Days 24 – 41)
Visit 1 (Day 1) → Visit 3 (Day 61)	60 days	53 days – 70 days (Days 54 – 71)
Visit 3 (Day 61) → Safety call 2 (Day 75)	14 days	11 days – 17 days (Days 72 – 78)

Visit 3 (Day 61) → Visit 4 (Day 91)	30 days	23 days – 40 days (Days 84 – 101)
-------------------------------------	---------	-----------------------------------

Safety call time intervals will not be used for the assessment of protocol deviations. The Study Day ranges shown in the table are based on optimal intervals; the actual Study Day ranges for Safety Call 2 and Visit 4 will be based on when Visit 3 occurs.

## 3.2 Study Endpoints

### 3.2.1 Primary Endpoints

Immune responses against *N. meningitidis* serogroup B\* test strains and *N. meningitidis* serogroups A, C, W-135, and Y, as measured by hSBA, 1 month after the last vaccination in all study groups

- hSBA GMTs against each of the *N. meningitidis* serogroup B test strains and against *N. meningitidis* serogroups A, C, W-135, and Y
- hSBA GMTs against all of *N. meningitidis* serogroup B test strains (pooled)
- Percentage of subjects with hSBA titers  $\geq$  the lower limit of quantitation (LLOQ) against each of the *N. meningitidis* serogroup B test strains and against *N. meningitidis* serogroups A, C, W-135, and Y
- Percentage of subjects with a 4-fold increase in hSBA titers against *N. meningitidis* serogroups B test strains and against *N. meningitidis* serogroups A, C, W-135, and Y
- hSBA geometric mean ratios (GMRs) against each of the *N. meningitidis* serogroup B test strains and against *N. meningitidis* serogroups A, C, W-135, and Y at 1 month after the last vaccination against baseline (Day 1)

\*Serogroup B strains that will be tested are M14459 (factor H binding protein; fHbp), 96217 (Neisserial adhesin A; NadA), NZ98/254 (PorA), and M07-0241084 (Neisseria heparin binding antigen; NHBA) and will be pooled to estimate the effect of immune interference due to stress to lymph nodes.

Note: A 4-fold rise is defined as:

- a) for individuals whose pre-vaccination titers are  $<$  the limit of detection (LOD), the post-vaccination titers must be  $\geq$ 4-fold the LOD or  $\geq$  the LLOQ, whichever is greater;
- b) for individuals whose pre-vaccination titers are  $\geq$  the LOD and  $<$  the LLOQ, the post-vaccination titers must be at least 4 times the LLOQ;

c) for individuals whose pre-vaccination titers are  $\geq$  the LLOQ, the post-vaccination titers must be at least 4 times the pre-vaccination titer.

The ratios of GMTs between study groups will be analyzed to evaluate effect of treatment as described below:

- a. Immune interference due to stress to lymph nodes (lymph-node effect) in rMenBOMV+ACWY\_S versus rMenBOMV+ACWY\_D study groups, on the pooled B strains, and individually by serogroup A, C, W-135, Y, and B test strains.
- b. Other unknown interference in the MenABCWY versus rMenBOMV+ACWY\_S study groups, by serogroup A, C, W-135, Y, and B test strains.
- c. The difference in immune response compared to control groups in rMenBOMV+ACWY\_S versus rMenBOMV and MenACWY, rMenBOMV+ACWY\_D versus rMenBOMV and MenACWY, and MenABCWY versus rMenBOMV and MenACWY study groups, by serogroup A, C, W-135, Y, and B test strains.

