### **10.4. *Determination of sample size***

The sample size is for exploratory statistical analysis purposes only. There are no formal confirmatory hypotheses to be tested. The text in this section describes what can be observed with the current sample size.

Sample size calculation was performed using PASS 12 and SAS 9.2 (SAS Institute Inc., Cary, NC, USA).

The potential immune interference due to immunological stress to lymph nodes is assumed to result in decreases to all of the 4 B test strains but to various extents. In a previous study (MenABCWY-011 [V102\_15]), the GMT ratios ranged from 74% (-0.13 on log10 scale) to 50% (-0.3 log10 scale) with a mean of 64% (-0.19 on log10 scale). Because of this consistent decrease in GMT ratios in the MenABCWY group in comparison to the MenB group across the 4 serogroups, the presence of the lymph-node effect will be tested globally on all the serogroups together. A multivariate analysis of V102\_15 data provided an estimate of  $\sigma = 0.435$  (on log10 scale) for the standard deviation (SD) of the averaged GMTs across the 4 serogroups of the MenABCWY arm. That variability is higher than what would be expected by dividing the variance of a single serogroup by 4 due to the correlations existing between serogroups.

Therefore, assuming a SD of  $\sigma = 0.435$  (in log form), group sample sizes of 100 in each study group will achieve a power of approximately 80% to reject the null hypothesis of equal means when the population mean difference is -0.130 (log GMT ratio 74%) with a SD of 0.435 for both groups and a significance level (alpha) of 10% using a 1-sided 2-sample equal-variance t-test. This calculation ignores the potential correlation that might exist between serogroups of the MenABCWY when pooled together.

The numerical results for the 2-sample t-test assuming equal variance (alternative hypothesis:  $\delta < 0$ ) is shown in [Table 14](#).

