## 8.1 Summary and Analysis of hSBA Geometric Mean Titer

### 8.1.1 Primary Endpoint

Titer results are not normally distributed so summary statistics will be calculated using log-transformed titer results. The anti-logarithm of the summary statistics will be presented. Titer results will be summarized by study group, visit (Baseline, AVISIT 4) for each serogroup (A, C, W-135, Y) and the four individual serogroup B test strains. Titer results will also be summarized for the pooled serogroup B test strains. Missing titer results and results below the LOD will be handled as described in Section 4.3. Unadjusted and adjusted summaries will be calculated and will be displayed in the same output.

In addition, the distribution of antibody titers for each serogroup (A, C, W-135, Y) and the individual serogroup B test strains will be displayed using reverse cumulative distribution curves. The x-axis of the reverse cumulative distribution curves will be presented on a log scale. A reference line will be included to show LLOQ. All study groups for a single visit will be displayed on the same page, and visits will be displayed on separate pages.

Unadjusted summaries will include the number of subjects with non-missing titer results, geometric mean titer (GMT), geometric standard deviation (GSD), 80% confidence interval (CI) for GMT, minimum and maximum.

GMT will be calculated as the anti-logarithm of the mean of the log-transformed titer values i.e. anti-logarithm of  $\sum(\log_{10}(\text{titer}))/n$  where  $n$  is the number of subjects with non-missing titer results. GSD will be calculated as the anti-

logarithm of the standard deviation (SD) of the log-transformed data. The 80% CI for GMT will be calculated as the anti-logarithm of the endpoints of the 80% CI for the mean of the log-transformed data. The anti-logarithm is calculated as  $10^x$  where  $x$  is the statistic of interest calculated from the log-transformed data (e.g. mean, SD, 80% CI endpoints).

Adjusted summaries will be calculated using an analysis of covariance (ANCOVA) model. The adjusted GMT, standard error (SE) and 80% CI from the ANCOVA model will be presented.

Two ANCOVA models will be fitted, ANCOVA1 and ANCOVA2. ANCOVA1 will be used to estimate adjusted summaries for individual serogroups A, C, W-135, Y and the individual serogroup B test strains. ANCOVA2 will be fitted to the serogroup B data only to obtain adjusted summaries for the pooled serogroup B test strains.

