### ANCOVA2

- The fixed-effect model will include age strata, study group, strain\*\* and center as fixed effects. The pre-vaccination (Baseline) log-transformed titer with centering at zero will be included as a continuous covariate. An interaction between strain\* and pre-vaccination log-transformed titer centered at zero will be included in the model.
- The model will be fitted to the serogroup B test strain data only.

\*\* a categorical variable will be used to indicate if the dependent variable (response) is for serogroup B test strain M14459, 96217, NZ98/254 or M07-0241084.

For each study group, adjusted GMTs, SEs and 80% CI for GMT will be obtained by taking the anti-logarithm of the least squares means, the SE and the lower and upper limits of the 80% CIs of the log-transformed titers. The pre-vaccination log-transformed titer will be zero centered as follows: *log-transformed titer for each subject at Baseline – mean(log-transformed titer for all subjects at Baseline)* i.e. centering will occur after the titer results have been log transformed.

The contrasts in Table 6 will be computed at AVISIT 4 based on PPS3 to investigate possible effects on the immune response based on strains common to each study group.

No adjustment will be made for multiple comparisons.

rMenBOMV+ACWY\_S will be declared statistically inferior if the 2-sided 80% CIs of the ratio of the GMT with rMenBOMV+ACWY\_D as control is lower than 1 at 1 month after last vaccination. The lymph-node effect would therefore be the most probable cause for the decrease observed.

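### A pooled serogroup B ratio with its own 80% CI is planned only for same-arm versus different-arm injection, not for the MenABCWY comparisons

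*SAP*

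**What the plan says.** S and D stand for rMenBOMV+ACWY_S and rMenBOMV+ACWY_D.

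SAP 3.2.1 sets three families of GMT ratios. Item a, S versus D, is analysed "on the pooled B strains, and individually by serogroup A, C, W-135, Y, and B test strains". Item b begins "Other unknown interference in the MenABCWY versus" S and goes by serogroup and B strain, with no mention of pooling. Item c, the comparisons with the single-vaccine controls, ends "and MenABCWY versus rMenBOMV and MenACWY study groups, by serogroup A, C, W-135, Y, and B test strains", again without pooling. SAP 3.2.2 and Protocol 10.1 and 10.2 follow the same pattern.

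SAP Table 7 (secondary) gives the pooled B strains and ANCOVA2 to S versus D only; every other B contrast there is individual strains with ANCOVA1. Table 6 (primary) shows MenABCWY versus rMenBOMV and D versus rMenBOMV as individual strains with ANCOVA1.

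On the model, SAP 8.1.1 says "ANCOVA2 will be fitted to the serogroup B data only to obtain adjusted summaries for the pooled serogroup B test strains". Group-level results are planned for every arm: "For each study group, adjusted GMTs, SEs and 80% CI for GMT will be obtained by taking the anti-logarithm" of the least squares results.

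On purpose, SAP section 1 says "The purpose of the current study is to evaluate whether there is immune interference when MenABCWY" is given. On the reason for a global test over strains, Protocol 10.4 says "Because of this consistent decrease in GMT ratios in the MenABCWY group in comparison to the MenB group across the 4 serogroups".

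**The concern.** The comparison that motivated pooling is MenABCWY against the MenB vaccine. The earlier strain ratios of 74% to 50% (mean 64%) come from it. The pooled contrast is nevertheless given only to S versus D, and neither of those arms receives MenABCWY.

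On the log scale the total shortfall splits exactly:

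log(MenABCWY/rMenBOMV) = log(MenABCWY/S) + log(S/D) + log(D/rMenBOMV)

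The middle term is the lymph-node effect and the first is the competing explanation, other interference. Under the plan the lymph-node term gets a global estimate with an interval. The other two terms and the total get four separate strain estimates each. At stake is how evenly the competing explanations are estimated when the results are read side by side, since the SAP attaches a causal reading to the S versus D result.

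**Working it through.** **1. Reproduce the plan's figure.** Inputs from Protocol 10.4: SD 0.435 log10 for the four-strain average, 100 per group, difference -0.130, one-sided alpha 0.10, equal-variance t-test.

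- Standard error = 0.435 × sqrt(2/100) = 0.0615
- Noncentrality = 0.130 / 0.0615 = 2.11, df = 198
- Power from the noncentral t = 0.796, as in Table 14. All 16 rows of that table reproduce to three decimals.
- At the earlier mean effect of -0.19, power is 0.964.
- Half-width of the two-sided 80% CI = 0.0791 log10.

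A pooled MenABCWY contrast with the same SD and group size would have these same properties.

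**2. Single-strain SD.** The documents give neither this SD nor the between-strain correlation. Assume four strains with equal variance and common correlation rho. The variance of the average is then SD² × (1 + 3 rho)/4, so

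single-strain SD = 0.435 × sqrt(4 / (1 + 3 rho))

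**3. Single-strain results** (100 per group, one-sided 10%):

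| rho | SD | Power at -0.13 | Power at -0.19 | 80% CI half-width |
|---|---|---|---|---|
| 0 | 0.870 | 0.41 | 0.60 | 0.158 |
| 0.2 | 0.688 | 0.52 | 0.75 | 0.125 |
| 0.5 | 0.550 | 0.65 | 0.88 | 0.100 |
| 0.8 | 0.472 | 0.75 | 0.94 | 0.086 |
| 1 (equals pooled) | 0.435 | 0.796 | 0.964 | 0.079 |

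Narrowing from pooling: 1 - 0.0791/0.0858 = 8% at rho 0.8, and 1 - 0.0791/0.1251 = 37% at rho 0.2.

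For scale, take an observed ratio of 0.64. The pooled factor is 10^0.0791 = 1.20, giving an 80% CI of about 0.53 to 0.77. A single strain at rho 0.2 has factor 10^0.1251 = 1.33, giving about 0.48 to 0.85.

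**4. Unequal effects.** A strain with the largest earlier drop (-0.30) has power 0.875 even at rho 0. It matches the pooled test at the mean effect of -0.19 when its SD is 0.435 × 0.30/0.19 = 0.687, that is rho = (4 × (0.19/0.30)² - 1)/3 = 0.20. Above that correlation the single strain does better. The power loss is therefore a statement about equal effects.

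**5. What the planned outputs already allow.** Within each B strain, all four terms of the identity are planned contrasts from one ANCOVA1 fit, so the split is exact there. On the pooled scale, dividing the ANCOVA2 adjusted GMTs of two groups gives the model's own point ratio. The interval does not follow from the reported group SEs: the least squares means share covariate and center estimates, so their covariance is needed.

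**The case against.** A reader might infer that the trial cannot say what part of the MenABCWY shortfall is lymph-node related, or that the parts cannot be put on one scale. The documents do not support that. S versus D is planned strain by strain as well as pooled, so the decomposition is available four times over, and pooled point ratios can be formed from planned outputs.

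The restriction also has a rationale. The plan assumes that lymph-node stress lowers all four B responses, and says the strains are pooled to estimate that effect. It makes no such assumption for other interference, which could be specific to one antigen. The earlier strain effects differed more than twofold on the log scale (-0.13 to -0.30), so strain-level estimates are defensible. ANCOVA2 has no group-by-strain term and would report one effect averaged over strains. This supports keeping the per-strain contrasts; it does not argue against adding a pooled one with that caveat.

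The study is exploratory, its analyses are described as descriptive, and only S versus D has a decision rule. For the other contrasts, lower power means mainly wider descriptive intervals. That stands and limits the importance of the point.

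Finally, Protocol 10.8 describes a pooled B analysis and lists contrasts a to h without confining pooling to the first. The available text of Table 6 has blank strain cells for MenABCWY versus S and S versus rMenBOMV. The restriction therefore rests mainly on SAP 3.2.1, 3.2.2 and Table 7, which agree with each other.

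**Conclusion.** The point holds as a cheap improvement. The SAP plans a pooled B ratio with its own 80% CI for S versus D only. MenABCWY versus S, MenABCWY versus rMenBOMV and D versus rMenBOMV are planned strain by strain, although the study's question and the case for pooling concern MenABCWY.

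At an equal effect across strains the per-strain estimates are less precise for any correlation below 1. The size rests on step 2's assumptions, applies the planning SD to every contrast, and changes with a correlation the documents do not state. A strain with a larger true drop can be well powered alone. No bias or error in the S versus D analysis is shown.

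**What to change.** Keep all per-strain contrasts. Add rows for pooled B strains with ANCOVA2 to SAP Tables 6 and 7 for:

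- MenABCWY versus rMenBOMV+ACWY_S
- MenABCWY versus rMenBOMV
- rMenBOMV+ACWY_D versus rMenBOMV

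rMenBOMV+ACWY_S versus rMenBOMV is optional, since on the log scale it is the sum of S versus D and D versus rMenBOMV. Amend items b and c of SAP 3.2.1 and 3.2.2 to match.

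Report the ratios with 80% CIs beside the pooled S versus D ratio, labelled descriptive. State that each is an average over strains whose effects may differ, and should be read with the strain-level ratios.

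The cost is a few extra contrast statements in a model already being fitted, plus table rows. Sample size, data and model do not change. Specifying the rows before analysis avoids a post hoc choice.
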